Simulations show that a total of 285 evaluable participants per active group in each cohort are needed to have 90% power to demonstrate non-inferiority in terms of neutralizing antibody GMT and seroresponse

^{*} Based on Day 15 VNA A2 results obtained from Cohort 2, Group 14 in study VAC18193RSV1004.

rates between high-risk adults aged 18 to 59 years and adults aged 65 years and older. With this sample size, the power to demonstrate non-inferiority in terms of neutralizing antibody GMT and seroresponse rates between all adults aged 18 to 59 years and adults aged 65 years and older is >95%. The power to demonstrate non-inferiority for the high-risk adults aged 18 to 59 years and adults aged 65 years and older is approximately 90%, taking into account the testing strategy (sequential testing). To account for exclusions from the Per-protocol Immunogenicity (PPI) Set, drop-outs, and missing samples, approximately 315 participants per active group should be enrolled.

Safety Analysis

Solicited AEs, unsolicited AEs, SAEs and AESIs will be collected in all participants.

In Cohorts 1 and 2, a placebo group (Groups 2 and 4) of approximately 70 high-risk adults aged 18 to 59 years and of approximately 70 healthy adults aged 18 to 59 years is added for blinding purposes. In Cohort 3, a placebo group (Group 6) of approximately 28 adults aged 65 years and older is added for blinding purposes.

Populations for Analysis Sets

The Full Analysis (FA) Set will include all participants who received study vaccine, regardless of the occurrence of protocol deviations and vaccine type (study vaccine or placebo). All safety and participant information analyses will be based on the FA Set.

The PPI Set will include all randomized participants who received study vaccine and for whom immunogenicity data are available. Samples taken after a participant experienced a major protocol deviation expected to impact the immunogenicity outcomes will be excluded from the PPI Set.

The list of major protocol deviations that would lead to elimination from the immunogenicity analysis will be specified in the Statistical Analysis Plan (SAP) or major protocol violation criteria document, which will be finalized before database lock and unblinding.

The primary analysis set for analyses related to RSV immunogenicity is the PPI Set. As a sensitivity analysis, key tables may also be based on the FA Set.

Immunogenicity Analyses

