- b. An early exit visit will be conducted as soon as possible for those participants who are unable to continue participation in the study and withdraw from the study before Day 183, but who do not withdraw consent. Participants who wish to withdraw consent from participation in the study will be offered an early exit visit (prior to formal withdrawal of consent).
- c. Signing of the ICF should be done before any study-related activity.
- d. Prestudy therapies administered up to 30 days pre-vaccination must be recorded on Day 1.
- e. For participants of childbearing potential only. The pregnancy test must be performed on the day of vaccination.
- f. A physical examination, including height and body weight, will be carried out on Day 1. At any other clinic visit, an abbreviated, symptom-directed examination will be performed if deemed necessary by the investigator based on any clinically relevant issues, clinically relevant symptoms, and medical history.
- g. Sitting systolic and diastolic blood pressure, heart rate, and respiratory rate after at least 5 minutes rest on Day 1. At non-vaccination visits, vital signs will be measured if deemed necessary by the investigator.
- h. Investigator must check for clinically significant acute illness at the time of vaccination or body temperature ≥38.0°C (≥100.4°F) within 24 hours prior to the planned time of vaccination. In such cases, the participant may be vaccinated up to, and no later than 10 days after the scheduled vaccination, or be withdrawn at the discretion of the investigator. Note that the pregnancy test must be repeated prior to vaccination.

- i. Blood for cellular immune responses at the time points indicated will be drawn only from Cellular Immuno Subset participants.
- j. After vaccination, participants will remain under observation at the study site for at least 30 minutes for presence of any acute reactions and solicited events. Any unsolicited AEs, solicited local (injection site) or systemic AEs, and vital signs (systolic and diastolic blood pressure [sitting], heart rate, respiratory rate after at least 5 minutes rest, and body temperature) will be documented by study-site personnel following this observation period.
- k. AESIs, including potential AESIs, are to be reported to the sponsor from the moment of vaccination until 6 months after the vaccination. See Section 8.3.6.

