4. STUDY DESIGN

4.1. Overall Design

This is a randomized, double-blind, placebo-controlled, multicenter, interventional Phase 3 study to evaluate the safety and immunogenicity of the Ad26/protein preF RSV vaccine in adults aged 18 to 59 years, including those who are at high-risk of severe RSV disease. A cohort of adults aged 65 years and older will also be included. A target of 1,113 participants will be enrolled: 385 healthy adults aged 18 to 59 years will be enrolled in Cohort 1 and randomized in a 9:2 ratio to receive Ad26/protein preF RSV vaccine or placebo; 385 high-risk adults aged 18 to 59 years will be enrolled in Cohort 2 and randomized in a 9:2 ratio to receive Ad26/protein preF RSV vaccine or placebo, 343 adults aged 65 years and older will be enrolled in Cohort 3 and randomized in a 45:4 ratio to receive Ad26/protein preF RSV vaccine or placebo (see Table 1). The study vaccine will be administered as a single IM injection.

Participants will be stratified for COVID-19 vaccine administration (3 categories: 1. Janssen COVID-19 vaccine, 2. Vaxzevria[®] [Oxford/AstraZeneca], 3. other vaccine, or no vaccine).

Table 1: Overview of the Cohorts, Groups, and Targeted Number of Participants				
Cohort		Group	N	Day 1 (Vaccination)
1	healthy adults, 18 to 59 years	1	315	Ad26.RSV.preF 1×10 ¹¹ vp + RSV preF protein 150 μg
		2	70	Placebo
2	high-risk adults, 18 to 59 years ^a	3	315	Ad26.RSV.preF 1×10 ¹¹ vp + RSV preF protein 150 μg
		4	70	Placebo
3	adults, 65 years and older	5	315	Ad26.RSV.preF 1×10 ¹¹ vp + RSV preF protein 150 μg
		6	28	Placebo

N = number of participants, vp = virus particles.

In all cohorts, participants will be stratified for COVID-19 vaccine administration.

All cohorts will be enrolled in parallel. Enrollment in Spain will be limited to Cohorts 2 and 3.

Safety and humoral immunogenicity assessments will be performed for all participants (see Section 9.2.1 for the sample size determination).

For a subset of the participants, additional cellular immunogenicity assessments will be performed. This subset will be referred to as the Cellular Immuno Subset and will consist of approximately 63 active study vaccine participants and approximately 7 placebo participants per cohort. The Cellular Immuno Subset will be recruited in specific study sites.

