4.2. Scientific Rationale for Study Design

For the rationale for performing this study, refer to Section 2.1.

Blinding and Control

A placebo control will be used to establish the frequency and magnitude of changes in clinical endpoints that may occur in the absence of active study vaccine in Cohorts 1 and 2. Safety of the vaccine in older adults has been established in the VAC18193RSV2001 study, therefore only a small placebo control group is added for blinding purposes. Within a cohort, randomization will be used to minimize bias in the assignment of participants to vaccination groups (active or placebo), to increase the likelihood that known and unknown participant attributes (eg, demographic and baseline characteristics) are evenly balanced across vaccination groups. Blinded vaccine will be used to reduce potential bias during data collection and evaluation of safety endpoints.

Vaccination Groups

The dose of each vaccine will be identical in the active groups (Groups 1, 3 and 5). Groups 2, 4 and 6 will receive placebo.

Vaccine Component Selection

The rationale behind the selection of the Ad26/protein preF RSV vaccine is described in Section 2.2 and in the IB for Ad26/protein preF RSV vaccine (IB Ad26/protein preF RSV vaccine 2021).

Dose Level Selection

The rationale behind the dose level selection for the Ad26/protein preF RSV vaccine is described in Section 4.3.

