6.3. Measures to Minimize Bias: Randomization and Blinding

Study Vaccine Allocation

Procedures for Randomization

Central randomization will be implemented in this study. Participants will be randomly assigned to a vaccination group based on a computer-generated randomization schedule prepared before the study by or under the supervision of the sponsor. The randomization will be balanced by using randomly permuted blocks.

The randomization will be stratified based on the COVID-19 administration vaccine (3 categories: 1. Janssen Covid-19 vaccine, 2. Vaxzevria (Oxford/AstraZeneca), 3. other vaccine or no vaccine).

Sites will be split into 2 categories based on their PBMC collection capabilities for enrolment in the Cellular Immuno Subset.

For Cohorts 1 and 2, sites collecting PBMC samples will initially randomize participants in the Cellular Immuno Subset of the respective cohort according to a 9:1 ratio (active: placebo). When the Cellular Immuno Subset has been completed for a cohort (70 participants per cohort), the sites will keep randomizing the remaining participants of that cohort according to a 4:1 ratio (active: placebo). Sites with no PBMC sample collection capabilities will randomize participants that are not part of the Cellular Immuno Subset (from whom only humoral samples will be collected) of the respective cohort according to a 4:1 ratio (active: placebo).

For Cohort 3, sites collecting PBMC samples will initially randomize participants in the Cellular Immuno Subset according to a 9:1 ratio (active: placebo). When the Cellular Immuno Subset has been completed (70 participants), the sites will keep randomizing the remaining participants of that cohort according to a 12:1 ratio (active: placebo). Sites with no PBMC sample collection capabilities will only randomize participants that are not part of the Cellular Immuno Subset (from whom only humoral samples will be collected) according to a 12:1 ratio (active: placebo).

In this way, the overall randomization ratio in Cohorts 1 and 2 is 9:2 (active:placebo) and 45:4 (active:placebo) in Cohort 3.

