9.4.4. Safety Analyses

No formal statistical testing of safety data is planned. Safety data (including solicited and unsolicited AEs) will be analyzed descriptively by cohort and group. All safety analyses will be based on the FA Set.

AEs

The verbatim terms used in the eCRF by investigators to identify AEs will be coded using the Medical Dictionary for Regulatory Activities (MedDRA). All reported AEs with onset during the active phase (ie, AEs occurring from the time of vaccination up to 28 days post-vaccination), and all SAEs and AESIs will be included in the analysis. For each AE, the number and percentage of participants who experience at least 1 occurrence of the given event will be summarized by group.

Summaries, listings, datasets, or participant narratives may be provided, as appropriate, for those participants who die, who discontinue study vaccination due to an AE, or who experience a severe AE, an SAE, or an AESI.

Summaries and/or listings may be provided separately for AEs with onset outside the above defined timeframe (ie, beyond 28 days post-vaccination).

Solicited local (injection site) and systemic AEs will be summarized descriptively. The overall frequencies per group as well as frequencies according to severity and duration will be calculated for solicited AEs. In addition, the number and percentages of participants with at least 1 solicited local (injection site) or systemic AE will be presented. Frequencies of unsolicited AEs, separately for all and vaccination-related only, will be presented by System Organ Class and preferred term.

Vital Signs

Baseline and emerging vital signs abnormalities will be listed.

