# 5.4. Primary Safety Endpoint Analysis

Safety endpoints include:

- Solicited local (injection site) and systemic AEs for 7 days after vaccination
- Unsolicited AEs for 28 days after vaccination
- Serious adverse events (SAEs) and adverse events of special interest (AESIs) until 6 months after vaccination

No formal statistical testing of safety data is planned. Safety data will be analyzed descriptively by cohort and group. All safety analyses will be based on the FA Set. Continuous variables will be summarized using the following statistics, as appropriate: number of observations, median, minimum and maximum. Frequencies and percentages (one decimal place) will be generated for categorical variables.

Safety data will be analyzed by study intervention regimens as designed per protocol, per phase and across the entire study period where applicable. For unsolicited AE, denominator for the percentages is the number of participants in the considered population and phase for a certain regimen (incidence per 100 participants/phase). For solicited AEs, the denominator for the percentages is the number of participants with data assessed by the PI in the considered population and phase for a certain and phase for a certain regimen (incidence per 100 participants/phase).

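### Do the unequal allocation ratios inside and outside the Cellular Immuno Subset bias the safety comparison with placebo in Cohorts 1 and 2?

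*Protocol*

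**What the plan says.** Protocol Section 6.3 governs allocation in Cohorts 1 and 2. At sites with PBMC capability, "sites collecting PBMC samples will initially randomize participants in the Cellular Immuno Subset of the respective cohort according to a 9:1 ratio (active: placebo". Once a cohort's subset of 70 is full, "the sites will keep randomizing the remaining participants of that cohort according to a 4:1 ratio (active: placebo". Sites without PBMC capability use 4:1 throughout. Section 4.1 adds that the subset "will consist of approximately 63 active study vaccine participants and approximately 7 placebo participants per cohort" and comes from particular sites.

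On the purpose of placebo, Section 4.2 says, for these two cohorts, "A placebo control will be used to establish the frequency and magnitude of changes in clinical endpoints" that may occur without active vaccine. The Synopsis says that the group "of approximately 70 healthy adults aged 18 to 59 years is added for blinding purposes", and Section 9.2.2 agrees with the Synopsis.

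On analysis, Protocol Section 9.4.4 says "Safety data (including solicited and unsolicited AEs) will be analyzed descriptively by cohort and group", and SAP Section 5.4 says "Safety data will be analyzed descriptively by cohort and group". Both rule out formal testing of safety data. SAP Section 5.6.1 lists only two age bands as subgroups. Neither safety section mentions subset membership. Table specifications are in a separate document (SAP Section 1) that is not available here.

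**The concern.** When the allocation ratio changes across a stratum, the pooled arms are not balanced on that stratum. Here the active arm has twice the subset share of the placebo arm. If subset members report more AEs, because of their sites, their earlier enrolment at those sites or their larger blood draws, the active column is raised slightly more than the placebo column. The vaccine would then look a little more reactogenic than it is.

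Safety in both cohorts is a primary objective, and Section 4.2 treats placebo as the reference for what happens without vaccine. Readers will set the two columns side by side whether or not a test is planned. The SAP stratifies the seroresponse analysis by COVID-19 vaccine category, for which the protocol states no difference in ratio, yet makes no allowance for the one factor across which the ratio does change.

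**Working it through.** **Inputs.** From Protocol Sections 4.1 and 6.3: 385 per cohort, subset of 70, 9:1 inside and 4:1 outside. The AE-rate gap D between subset and non-subset is not in the documents and is assumed.

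**1. Reproduce the plan's ratio.**
- Subset: 70 × 9/10 = 63 active, 7 placebo.
- Remainder: 385 − 70 = 315, split 252 active and 63 placebo.
- Total: 315:70 = 9:2, as stated in Section 6.3.

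**2. Subset shares.** Active 63/315 = 0.20; placebo 7/70 = 0.10. The split is only approximate. With 5 placebo among the 70, the share difference is 65/315 − 5/70 = 0.135; with 9 it is 61/315 − 9/70 = 0.065.

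**3. Bias of the crude difference.**
- Same gap D in both arms: 0.10 × D.
- Unequal gaps: take as target the difference standardised to the whole cohort, where the subset share is 70/385 = 0.182. The bias is (0.200 − 0.182) × active gap + (0.182 − 0.100) × placebo gap = 0.018 × active gap + 0.082 × placebo gap.

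**4. Size, with no vaccine effect and equal gaps.**

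| Outside | Inside | Active v placebo | Bias (points) | Standard error (points) | Bias/SE |
|---|---|---|---|---|---|
| 30% | 35% | 31.0% v 30.5% | 0.5 | 6.09 | 0.08 |
| 30% | 40% | 32.0% v 31.0% | 1.0 | 6.12 | 0.16 |
| 30% | 50% | 34.0% v 32.0% | 2.0 | 6.18 | 0.32 |
| 10% | 15% | 11.0% v 10.5% | 0.5 | 4.07 | 0.12 |
| 10% | 20% | 12.0% v 11.0% | 1.0 | 4.16 | 0.24 |

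At a common rate p, the 95% half-width is 1.96 × √[p(1 − p)(1/315 + 1/70)]: 7.8 points at 10% and 11.9 points at 30%.

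**5. Would a stratified difference be better?** The Mantel-Haenszel (MH) weights are 63 × 7/70 = 6.3 for the subset and 252 × 63/315 = 50.4 outside it. The subset therefore gets 6.3/56.7 = 11% of the weight, although it is 18.2% of the cohort.

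- *Equal gaps.* MH removes the bias. Its variance factor is (1/81)(1/63 + 1/7) + (64/81)(1/252 + 1/63) = 0.01764, against 0.01746 for the crude difference, a rise of 1.0%. MH has the smaller mean squared error only when (0.10 × D)² exceeds the added variance, p(1 − p) × 0.000176. That needs D above about 4 points at p = 10% and about 6 points at p = 30%.
- *Unequal gaps.* Assume active 70% inside and 50% outside, placebo 25% and 20%. Crude: 54.0 − 20.5 = 33.5 points. The stratum differences are 45 and 30. Standardised: 30 + 0.182 × 15 = 32.7. MH: 30 + 15/9 = 31.7. The crude figure is 0.8 too high and MH is 1.1 too low.
- *Break-even.* Relative to the standardised difference, MH is off by (1/9 − 2/11) = −0.071 times (active gap − placebo gap). For positive gaps, this exceeds the crude bias once the active gap is more than about 2.9 times the placebo gap.
- *Cohort weights instead of MH weights.* These hit the target by construction. The variance factor is (2/11)²(1/63 + 1/7) + (9/11)²(1/252 + 1/63) = 0.01853, about 6% above crude.

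**6. What could create D?** The visit schedule, diary and AE recording in Section 1.3 are the same for everyone. The scheduled difference is the extra sample: "Blood for cellular immune responses at the time points indicated will be drawn only from Cellular Immuno Subset participants", which makes 60 mL rather than 20 mL per draw. The Day 1 draw precedes vaccination. The next is at Day 15 (±3 days), after the 7-day solicited period. Site habits and enrolment time can act only through D, because allocation outside the subset is 4:1 at both site types.

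**7. Reach.** The non-inferiority comparisons use Groups 1, 3 and 5, each with a planned subset share of 63/315 = 20%, so this imbalance does not touch them.

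**The case for a change.** The best case for a change is that the imbalance is built into the design, placebo is named as the reference, and the correction is small: a descriptive MH risk difference for four AE categories in two cohorts, eight entries, with about 1% more variance if D is zero. The SAP already uses this kind of weighting for seroresponse. A non-zero D is also plausible. Subset members come from selected sites and give more blood, Section 2.3.1 lists pain, bruising, dizziness and syncope among blood-draw effects, and the Day 15 draw falls inside the 28-day unsolicited window.

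The shares stand, and so does the caution to anyone reading the two columns against each other. The claim of a cheap correction does not stand in general. It relies on a constant risk difference across strata, which is doubtful for solicited events: if local reporting habits scale with reactogenicity, the gap is wider in the active arm. The MH subset stratum also rests on about 7 placebo recipients per cohort, where one event moves the rate by 14.3 points.

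**Conclusion.** No change is needed. The design places about 20% of active and 10% of placebo recipients in the subset in Cohorts 1 and 2. With an equal gap in both arms, an informal comparison carries about 0.10 × D: 0.5 to 2.0 points for assumed gaps of 5 to 20 points, or 0.08 to 0.32 standard errors in the cases worked. D has no documented value and may be zero.

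No planned result is wrong. Each group's percentage is correct for that group, and the protocol and SAP set out no active-placebo safety contrast. Adding one would introduce an unplanned estimate, bring a gain only if D exceeds roughly 4 to 6 points and is similar in both arms, and leave what the trial can conclude unchanged. The two descriptions of the placebo groups' purpose do not alter this, since a group added for blinding can also serve as a descriptive reference. The conclusion rests on the planned counts and on the visible text; the separate table specifications were not available.

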6.4. Study Vaccination Compliance

Ad26/protein preF RSV vaccine or placebo will be administered IM by blinded qualified study-site personnel at the study site. Details of the administration will be recorded in the eCRF (including date and time of injection, and site of administration). For blinding procedures, see Section 6.3.

6.5. Dose Modification

Not applicable.

6.6. Continued Access to Study Vaccine After the End of the Study

Participants will be instructed that study vaccine will not be made available to them after they have completed/discontinued study vaccination.

6.7. Treatment of Overdose

For this study, any dose of the Ad26/protein preF RSV vaccine greater than the protocol-specified dose will be considered an overdose. The sponsor does not recommend specific treatment for an overdose.

In the event of an overdose, the investigator or treating physician should:

- Contact the Medical Monitor immediately.
- Closely monitor the participant for AEs/SAEs/AESIs until resolution.
- Document the quantity of the excess dose in the eCRF.
- Report as a special reporting situation.

6.8. Concomitant Therapy

Prestudy therapies administered within the 30 days before administration of the study vaccine must be recorded on Day 1. Additionally, any history of SARS-CoV-2 vaccination (name/manufacturer of the vaccine and date of administration, whenever possible) prior to and during the study will be collected in the eCRF.

Concomitant therapies associated with solicited AEs will be collected by the participants in the participant diary from the time of study vaccination through 7 days after vaccination. Concomitant therapies associated with unsolicited AEs will be collected and recorded in the eCRF from the time of study vaccination through 28 days after vaccination. Concomitant therapies associated with SAEs or AESIs will be collected and recorded in the eCRF from ICF signature until 6 months after vaccination.

Analgesic/antipyretic medications and non-steroidal anti-inflammatory drugs may be used post-vaccination only in cases of medical need (eg, fever or pain) and their use must be documented. Use of these medications as routine prophylaxis prior to study vaccination is discouraged.

Information on concomitant use of herbal supplements or vitamins will not be collected.

Use of any experimental medication (including experimental vaccines other than the study vaccine) during the study is not allowed.

Vaccination with licensed live attenuated vaccines within 28 days of a study vaccination (ie, before or after) is prohibited. Other licensed (not live) vaccines (eg, influenza, tetanus, hepatitis A, hepatitis B, rabies) should be given at least 14 days before (or at least 14 days after) administration of study vaccine in order to avoid potential confusion of adverse reactions and potential immune interference. If a vaccine is indicated in a postexposure setting (eg, rabies or tetanus), it must take priority over the study vaccine.

For SARS-COV-2 vaccines either licensed or available under Emergency Use Authorization: live attenuated vaccines should be given at least 28 days before or after vaccination; non-live vaccines should be given at least 14 days before or after vaccination.

A viral-vectored SARS-COV-2 vaccine is not to be given within 28 days prior to randomization or during the study period until 28 days after the study vaccination.

Use of systemic corticosteroids^a must be documented until 14 days after study vaccination. Antineoplastic and immunomodulating agents, eg, cancer chemotherapeutic agents, or systemic corticosteroids, or radiotherapy are prohibited until 14 days after study vaccination. If the use of systemic corticosteroids, antineoplastic or immunomodulating agents or any therapy described in exclusion criterion 7 becomes medically indicated during the study for any participant, the sponsor should be notified.

The sponsor must be notified in advance (or as soon as possible thereafter) of any instances in which prohibited therapies are administered.

